4.3. Plasma Gelsolin and Treatment of CAP

Plasma gelsolin is a human protein produced and secreted by virtually every cell type, and it circulates at high levels in the blood of healthy individuals. At normal levels of 200-300 mg/L, it is the fourth most abundant protein in the circulation.

The therapeutic protein being developed by BioAegis Therapeutics, Inc. (BioAegis or Sponsor) is recombinant human plasma gelsolin (rhu-pGSN) and was formerly referred to as BG9385. It is identical to the complete natural protein and is comprised of 755 amino acids. The protein, like the natural protein, is non-glycosylated. The protein consists of six repeated domains, which make up three distinct actin binding sites, two that bind globular actin (G-actin) and one that binds filamentous actin (F-actin). Domain 1 plus the first 10 amino acids of domain 2 of gelsolin is the minimal fragment size required for its actin severing activity. Rhu-pGSN contains multiple calcium binding sites that regulate its activity. It is a highly conserved protein, as far back as *Drosophila*.

Plasma gelsolin modulates inflammation while at the same time, boosting the body's ability to clear pathogens. It functions through mechanisms quite distinct from anti-inflammatory agents, which are antagonists of specific mediators or inhibitors of specific enzymes. Plasma gelsolin functions through a pleiotropic mechanism of action, scavenging toxic actin, binding inflammatory mediators and enhancing pathogen clearance. pGSN levels decrease markedly in a variety of clinical conditions such as acute respiratory distress syndrome, sepsis, major trauma, prolonged hyperoxia, malaria, and liver injury. The strength of the correlation between magnitude of decline in pGSN and likelihood of mortality is especially striking (Lee et al, 2006; 2008; 2009; Osborn et al, 2008). Repletion of depressed plasma gelsolin levels with rhu-pGSN is expected to benefit patients through four distinct mechanisms that have been described in the literature:

1. *Sequestration of released actin from sites of damage.* This sequestration causes local depletion of pGSN while leaving large stores of pGSN continuing to circulate in healthy individuals. Modest reduction of systemic pGSN levels is then restored after healing is complete (Haddad et al, 1990; Lee et al, 1992).

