**List of Abbreviations**

Abbreviation	Description
AUC 0-t	The area under the plasma concentration-time curve, from time 0 (time of dosing) to the last time point with measurable analyte concentration, calculated by the log down, linear up trapezoidal method.
AE	Adverse Event
ATC	Anatomical Therapeutic Class
AUC 0-inf	The area under the plasma concentration-time curve from time 0 extrapolated to infinity. AUC 0-inf is calculated as the sum of AUC 0-t plus the ratio of the last measurable plasma concentration to the elimination rate constant ( $k_{el}$ ).
AUC 0-8	The area under the plasma concentration-time curve, from time 0 (time of dosing) to the 8 hours concentration, calculated by the log down, linear up trapezoidal method.
BLQ	Below the quantitation limit
CAP	Community-Acquired Pneumonia
CBC	Complete Blood Count
C max	Maximum observed concentration
C min	Minimum observed concentration over the dosing interval.
CL/F	Apparent clearance calculated as Dose/AUC 0-inf .
CS	Clinically Significant
CSR	Clinical Study Report
CV	Coefficient of variation
DLT	Dose Limiting Toxicity
DN_AUC 0-inf	Dose-normalized AUC 0-inf , calculated as AUC 0-inf divided by dose.
DN_AUC 0-t	Dose-normalized AUC 0-t , calculated as AUC 0-t divided by dose.
DN_AUC 0-8	Dose-normalized AUC 0-8 , calculated as AUC 0-8 divided by dose.
DN_C max	Dose-normalized C max , calculated as C max divided by dose.
EKG	Electrocardiogram
eCRF	Electronic Case Report Form
EOS	End of Study
GCP	Good Clinical Practice
geo CV	Geometric Coefficient of Variation
HIV	Human Immunodeficiency Virus
ITT	Intention-to-treat
IV	Intravenous
IWRS	Interactive web response system
k el	Apparent terminal elimination rate constant, calculated by linear regression of the terminal linear portion of the log concentration vs. time curve.
LLQ	Lower Limit of Quantification
MAD	Multiple-Ascending Dose
MedDRA	Medical Dictionary for Regulatory Activities
MMSE	Mini-Mental State Exam
N/A	Not Applicable
NCS	Not Clinically Significant

Abbreviation	Description
NK	Not Known
PE	Physical Examination
PI	Principal Investigator
PK	Pharmacokinetic
PP	Per Protocol
PSI	Pneumonia Severity Index
PT	Preferred Term
rhu-pGSN	Recombinant human plasma Gelsolin
SAE	Serious Adverse Event

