## 9. PHARMACOKINETICS (PK)

All PK summary tables and figures will be based on the PK Population. All listings will be based on the Safety Population (Actual Treatment). All analyses will be done by treatment group.

For the 1 dose in the SD arm and the first 2 doses in the MAD arms, blood will be drawn within 30 minutes pre-dose, and 5-10 minutes after the end of administration, as well as 2, 8, 12 and/or 16, and 24 hours after the end of administration ( $\pm$  30 minutes) for analysis. Identical PK sampling is encouraged on Day 3 where feasible (but not required) in the multiple-dose arms.

In this section (section 9):

- The rhu-pGSN treatment group will be referred to the Active treatment group.
- Exogenous pGSN concentrations will be referred to as rhu-pGSN concentrations.
- Endogenous pGSN + Exogenous pGSN (total) will be referred to as pGSN

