#### **Day 1: SD/MAD & Day 2/3: MAD**

AUC 0-t	The area under the plasma concentration-time curve, from time 0 (time of dosing) to the last time point (24 hours) with measurable analyte concentration, calculated by the log down, linear up trapezoidal method.  AUC 0-t will additionally be calculated for the estimated rhu-pGSN profile for both the change from pre-dose on each study day and the double-delta method.
AUC 0-8	The area under the plasma concentration-time curve, from time 0 (time of dosing) to the 8 hours concentration, calculated by the log down, linear up trapezoidal method.  AUC 0-8 will additionally be calculated for the estimated rhu-pGSN profile for both the change from pre-dose on each study day and the double-delta method.
AUC 0-inf	The area under the plasma concentration-time curve from time 0 extrapolated to infinity. AUC 0-inf is calculated as the sum of AUC 0-t plus the ratio of the last measurable plasma concentration to the elimination rate constant ( $k_{el}$ ).
C max	Maximum observed concentration.  C max will additionally be calculated for the estimated rhu-pGSN profile for both the change from pre-dose on each study day and the double-delta method.
T max	Time to maximum observed drug concentration. If the maximum value occurs at more than one time point, T max is defined as the first time point with this value.

$k_{el}$	Apparent terminal elimination rate constant calculated by linear regression of the terminal linear portion of the log concentration vs. time curve.
$t_{1/2}$	Apparent elimination half-life, calculated as $\ln(2)/k_{el}$
%AUC ext	Percentage of the extrapolated area under the plasma concentration-time curve, calculated as $100\% * [AUC_{0-inf} - AUC_{0-t}] / AUC_{0-inf}$
$C_L/F$	Apparent clearance calculated as $Dose/AUC_{0-inf}$ .
$V_z/F$	Apparent volume of distribution at the terminal phase, calculated as $Dose / (k_{el} \times AUC_{0-inf})$ .
DN_C max	Dose-normalized C max , calculated as C max divided by dose DN_C max will additionally be calculated for the estimated rhu-pGSN profile for both the change from pre-dose day 1 and the double-delta method..
DN_AUC 0-inf	Dose-normalized AUC 0-inf , calculated as AUC 0-inf divided by dose

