DN_AUC 0-t	Dose-normalized AUC 0-t , calculated as AUC 0-t divided by dose DN_AUC 0-t will additionally be calculated for the estimated rhu-pGSN profile for both the change from pre-dose on each study day and the double-delta method.
DN_AUC 0-8	Dose-normalized AUC 0-24 , calculated as AUC 0-24 divided by dose DN_AUC 0-8 will additionally be calculated for the estimated rhu-pGSN profile for both the change from pre-dose on each study day and the double-delta method.

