#### Analysis of Estimated rhu-pGSN

This analysis will exclude the placebo treatment group:

- Pre-dose values on each study day will be presented as recorded;
- Pre-dose values on each study day that are BLQ will be set to  $\frac{1}{2}$  LLQ;
- Subsequent BLQ values (post the first quantifiable concentration on each day) will be set to  $\frac{1}{2}$  LLQ.
- Estimated rhu-pGSN concentration  
= concentration on Day z at Time Point y – Day z Pre-dose concentration

Individual estimated rhu-pGSN concentrations will be summarized by nominal sampling time. Geometric summary statistics will not be calculated for estimated rhu-pGSN concentrations, as these values could be lower than or equal to 0.

Estimated Individual (for each subject) and mean estimated plasma rhu-pGSN concentration over time will be displayed graphically in linear plots of estimated rhu-pGSN concentration versus time. The actual collection time will be used for individual estimated plasma rhu-pGSN concentration curve and the nominal time will be used for plot of mean estimated plasma rhu-pGSN concentration curve.

Estimated plasma concentrations vs. time data will be analyzed using SAS software. Actual collection time will be used in the calculation of plasma PK parameters. The following parameters (including dose normalized parameters) will be calculated for each study day:

- $AUC_{0-t}$
- $AUC_{0-8h}$
- $C_{max}$

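### SAP Section 9.1 defines DN_AUC0-8 from AUC0-24, contradicting the SAP's own abbreviation list, parameter lists and listing shells

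*SAP*

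**What the plan says.** The parameter table in SAP Section 9.1 (Day 1: SD/MAD and Day 2/3: MAD) has a row labelled DN_AUC0-8. Its text describes a dose-normalised AUC0-24 and gives the formula as AUC "0-24 divided by dose", so the 24-hour interval appears twice in the row. The row then extends the parameter to the change-from-pre-dose and double-delta profiles of estimated rhu-pGSN.

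The List of Abbreviations in the same SAP defines the same label as AUC "0-8 divided by dose".

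The related rows of Section 9.1 are clear. AUC0-8 runs from dosing "to the 8 hours concentration, calculated by the log down, linear up trapezoidal method". AUC0-t runs from dosing "to the last time point (24 hours) with measurable analyte concentration". There is no row for AUC0-24.

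In Section 9.2, both subsections on estimated rhu-pGSN state: "The following parameters (including dose normalized parameters) will be calculated for each study day". Each then lists AUC0-t, AUC0-8h and Cmax. The programming notes to Tables 14.2.3.1 to 14.2.3.3 repeat that list. Listings 16.2.6.3.1 to 16.2.6.4.2 have a DN_AUC0-8 column and no AUC0-24 column.

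Protocol Section 5.2.2 names AUC0-8 among the secondary PK parameters. It does not name a dose-normalised form.

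**The concern.** The two definitions cannot both be followed, and the faulty one stands in the section that sets out how each PK parameter is calculated. Because the wrong interval occurs twice, the row reads as a coherent formula and not as an obvious slip. A program written from it would fill a column labelled 0-8 h with an area over 0-24 h.

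SAP Section 15.1 says that the final analysis follows the final SAP and that deviations are documented in the study report. If the row stays, the choice is between a mislabelled result and a documented departure from the plan.

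**Working it through.** **Step 1. Which reading the SAP supports.** For AUC0-8 divided by dose: the row label itself, the List of Abbreviations, the two parameter lists in Section 9.2, the notes to Tables 14.2.3.1 to 14.2.3.3, and the four listing shells. For AUC0-24 divided by dose: the text of one row in Section 9.1. The intended parameter is AUC0-8 divided by dose, and the row is very probably a copying error.

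**Step 2. What a literal program would return.** AUC0-24 has no definition of its own. When the last measurable sample is the 24 h one, it equals AUC0-t up to small differences from actual sampling times. The column would then nearly repeat DN_AUC0-t, which has its own row directly above.

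**Step 3. Size without a baseline.** The plan states no figure to reproduce. Dose cancels, so the inflation factor is AUC0-24 / AUC0-8. For a mono-exponential decline after an IV dose, with k = ln 2 / t½ and x = 2^(-8/t½):

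factor = (1 - e^(-24k)) / (1 - e^(-8k)) = 1 + x + x²

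| Assumed t½ (h) | x | Factor |
|---|---|---|
| 4 | 0.250 | 1.31 |
| 8 | 0.500 | 1.75 |
| 10 | 0.574 | 1.90 |
| 16 | 0.707 | 2.21 |
| 20 | 0.758 | 2.33 |

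The factor reaches 2 when x = 0.618, which is a half-life of 11.5 h. It tends to 1 for very short half-lives and to 3 (24/8) for a flat profile.

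These half-lives are assumptions. The only half-life in the documents is in Protocol Section 4.4.1: about 10 to 16 h for radioactivity in the lungs of rats and monkeys, which is not a human plasma value.

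**Step 4. Size with an endogenous baseline.** The main parameters are for total protein: "Endogenous pGSN + Exogenous pGSN (total) will be referred to as pGSN". With a constant baseline B and initial increment C0 = dose / V:

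factor = [24B + (C0/k)(1 - e^(-24k))] / [8B + (C0/k)(1 - e^(-8k))]

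The documents give no baseline for these patients. Protocol Section 4.3 gives a healthy range ("At normal levels of 200-300 mg/L") and says that levels fall in several illnesses. I assumed B from 50 to 300 mg/L, V from 0.04 to 0.10 L/kg and half-lives from 2 to 24 h, at 6, 12 and 24 mg/kg. The factor then runs from 1.45 (24 mg/kg, V 0.04, B 50, 2 h) to 2.91 (6 mg/kg, V 0.10, B 300, 24 h), mostly 2.0 to 2.9.

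Worked case with t½ 10 h, V 0.05 L/kg and B 100 mg/L at 6 mg/kg: C0 = 120 mg/L and C0/k = 1731, so the factor is (2400 + 1731 × 0.811) / (800 + 1731 × 0.426) = 3804 / 1537 = 2.47. The same inputs give 2.29 at 12 mg/kg and 2.14 at 24 mg/kg.

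**Step 5. Check with the SAP's integration rule.** I applied the log-down, linear-up trapezoidal rule to samples at 0, 0.125, 2, 8, 12 and 24 h with C0 = 300 mg/L. At half-lives of 4, 8, 10 and 16 h it gives 1.32, 1.76, 1.91 and 2.22 without baseline. With a baseline of 100 mg/L it gives 1.98, 2.17, 2.26 and 2.45. The brief rise from the pre-dose sample hardly matters.

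**The case against.** The strongest reply is that this is a slip that a competent programmer would catch. The row label is right, the abbreviation list is right, AUC0-24 is an undefined input, and several other places point to AUC0-8. That stands as a description of the likely cause and limits the seriousness. It does not remove the contradiction. For the total-pGSN profile, moreover, Section 9.2 gives no second parameter list to correct Section 9.1.

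The reply is also right against four stronger readings that a reader might infer.

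- **That the value would be about 2 to 3 times too large.** This needs a half-life and a baseline that the documents do not give. Once the pre-dose value is subtracted ("concentration on Day z at Time Point y – Day z Pre-dose concentration"), the factor is below 2 for any half-life under 11.5 h, and 3 is only the flat-profile limit.
- **That no dose-normalised AUC0-8 would be produced.** Several places in the SAP ask for one. The calculation is left ambiguous, not omitted.
- **That the error carries into all three profile versions.** The Section 9.1 row does mention all three, but the Section 9.2 lists for the two estimated profiles name AUC0-8h with its dose-normalised form. They conflict with the row; they do not inherit it.
- **That a planned dose-proportionality analysis is compromised.** Neither document plans one. The PK output is descriptive, and DN_Cmax, DN_AUC0-t and DN_AUC0-inf remain.

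One part of the reply is too generous: that applying the same rule at every dose leaves the comparison between doses intact. For total pGSN the factor need not be constant. In the worked case it falls from 2.47 at 6 mg/kg to 2.14 at 24 mg/kg, a relative shift of about 15% (2.47 / 2.14 = 1.15). That would affect an informal reading only.

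**Conclusion.** The contradiction is real, and the Section 9.1 row is wrong as written. Followed literally, it overstates DN_AUC0-8 by a factor of more than 1 and up to 3. This bound assumes a non-negative profile that does not rise after the injection. The SAP itself allows for estimated rhu-pGSN values at or below zero, and an endogenous level that recovers within 24 h would also break the assumption; in either case the factor could leave this range. Every point value within the range rests on assumed half-lives, baselines and volumes.

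The scope is narrow. AUC0-8 is correctly defined and unaffected, as are the primary safety endpoint and the other PK parameters. What is at risk is one derived, descriptive quantity. The row should be corrected because it sits in the defining section, not because any study conclusion depends on it.

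**What to change.** In the DN_AUC0-8 row of SAP Section 9.1, change both 0-24 subscripts to 0-8, so that the parameter is AUC0-8 divided by dose as in the List of Abbreviations. State that this holds for the total, change-from-pre-dose and double-delta profiles. If an area over 0-24 h is wanted, give it its own row and label, and say how it differs from AUC0-t.

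The cost is a one-line SAP correction before PK programming. No data collection, sample size or protocol endpoint changes, and the table and listing shells can stay as they are.

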## 9.2 Biostatistical methods

### Plasma pGSN

Individual plasma pGSN concentrations will be summarized by nominal sampling time.

Plasma pGSN concentrations that are below the quantitation limit (BQL) will be set to 0 if before the first quantifiable concentration, and to ½ the lower level of quantification elsewhere for calculation of summary statistics for concentration data at each time point.

The actual blood sampling dates and times relative to dosing time will be listed by subject and nominal sampling time, with time deviations calculated for all subjects with available plasma concentration data, including subjects excluded from the PK Population.

Individual (for each subject) and mean plasma pGSN concentration over time will be displayed graphically in linear and semi-logarithmic plot of pGSN concentration versus time. The actual collection time will be used for individual plasma pGSN concentration curve and the nominal time will be used for plot of mean plasma pGSN concentration curve.

Plasma concentrations vs. time data will be analyzed using validated PK software (Phoenix WinNonlin version 6.3 or higher), by standard non-compartmental model. Actual collection time will be used in the calculation of plasma PK parameters. For the calculation of the PK parameters, all plasma concentrations that are BLQ prior to the first measurable

concentration will be set to  $\frac{1}{2}$  the lower level of quantification. The BLQ values that are between measurable concentrations will be set to  $\frac{1}{2}$  LLOQ. The BLQ values that occur at the end of the profile (after the last quantifiable concentration) will also be set to  $\frac{1}{2}$  the lower level of quantification.

#### Ratio of Plasma pGSN

For subjects that do not have quantifiable pre-dose concentration values on each day, the pre-dose value will be set to  $\frac{1}{2}$  lower limit of quantification (LLQ).

Individual plasma pGSN: Day 1, 2 and Day 3 pGSN concentration ratios from each day's pre-dose will be summarized by nominal sampling time.

Plasma pGSN concentrations that are below the quantitation limit (BQL) will be set to  $\frac{1}{2}$  the lower level of quantification post dose for calculation of summary statistics for concentration ratio data at each time point.

#### Ratio of Pre-dose and Placebo Adjusted Plasma pGSN

For the active treatment groups, plasma concentration of pGSN will further be evaluated (adjusted) in terms of the mean Placebo pGSN at each time point as well as the pre-dose (baseline value) for each study day:

- Pre-dose values on each study day will be presented as recorded;
- Pre-dose values on each study day that are BLQ will be set to  $\frac{1}{2}$  LLQ;
- Subsequent BLQ values (post the first quantifiable concentration on each day) will be set to  $\frac{1}{2}$  LLQ.
- Pre-dose and Placebo Adjusted Concentration  
= (Active Treatment Group natural log Concentration on Day z at Time Point y – Day z Pre-dose natural log Concentration) - (Placebo Treatment Group natural log Concentration on Day z at Time Point y – Placebo Day z Pre-dose natural log Concentration) [results will be back-transformed to the ratio of ratios scale.]

Baseline and Placebo corrected Individual plasma pGSN concentrations will be summarized by nominal sampling time.

#### Analysis of Estimated rhu-pGSN

This analysis will exclude the placebo treatment group:

- Pre-dose values on each study day will be presented as recorded;
- Pre-dose values on each study day that are BLQ will be set to  $\frac{1}{2}$  LLQ;
- Subsequent BLQ values (post the first quantifiable concentration on each day) will be set to  $\frac{1}{2}$  LLQ.
- Estimated rhu-pGSN concentration  
= concentration on Day z at Time Point y – Day z Pre-dose concentration

Individual estimated rhu-pGSN concentrations will be summarized by nominal sampling time. Geometric summary statistics will not be calculated for estimated rhu-pGSN concentrations, as these values could be lower than or equal to 0.

Estimated Individual (for each subject) and mean estimated plasma rhu-pGSN concentration over time will be displayed graphically in linear plots of estimated rhu-pGSN concentration versus time. The actual collection time will be used for individual estimated plasma rhu-pGSN concentration curve and the nominal time will be used for plot of mean estimated plasma rhu-pGSN concentration curve.

Estimated plasma concentrations vs. time data will be analyzed using SAS software. Actual collection time will be used in the calculation of plasma PK parameters. The following parameters (including dose normalized parameters) will be calculated for each study day:

- $AUC_{0-t}$
- $AUC_{0-8h}$
- $C_{max}$

#### Double Delta Analysis of Estimated rhu-pGSN

- Pre-dose values on each study day will be presented as recorded;
- Pre-dose values on each study day that are BLQ will be set to  $\frac{1}{2}$  LLQ;
- Subsequent BLQ values (post the first quantifiable concentration on each day) will be set to  $\frac{1}{2}$  LLQ.
- Estimated rhu-pGSN will be calculated as follows:  
= (Active Treatment Group Concentration on Day z at Time Point y – Day z Pre-dose Concentration) - (Mean Placebo Treatment Group Concentration on Day z at Time Point y – Mean Placebo Day z Pre-dose Concentration)

Estimated rhu-pGSN concentrations will be summarized by nominal sampling time. Geometric summary statistics will not be calculated for estimated rhu-pGSN concentrations, as these values could be lower than or equal to 0.

Estimated Individual (for each subject) and mean estimated plasma rhu-pGSN concentration over time will be displayed graphically in linear plots of estimated rhu-pGSN concentration versus time. The nominal time will be used for individual estimated plasma rhu-pGSN concentration curve and the nominal time will be used for plot of mean estimated plasma rhu-pGSN concentration curve.

Estimated rhu-pGSN plasma concentrations vs. time data will be analyzed using SAS software. Nominal time will be used in the calculation of plasma PK parameters. The following parameters (including dose normalized parameters) will be calculated for each study day:

- $AUC_{0-t}$
- $AUC_{0-8h}$
- $C_{max}$

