Doses in the multiple-dose arms should be given at 24-hour (\pm 60-minute) intervals. For the one dose in the SD arm and the first 2 doses in the multiple-dose arms, blood will be drawn within 30 minutes predose, and 5-10 minutes after the end of administration, as well as 2, 8, 12 and/or 16, and 24 hours after the end of administration (\pm 30 minutes) for analysis of plasma for maximum concentration (C_{max}), time to maximum concentration (T_{max}), terminal half-life ($T_{1/2}$), area under the curve from time zero to 8 hours (AUC_{0-8}), and area under the curve from time zero to infinity (AUC_{inf}). Sampling at both the 12- and 16-hour time points is encouraged where feasible, but only one of these two times is required. Identical PK sampling is encouraged on Day 3 where feasible, but not required in the multiple-dose arms. In the multiple-dose arms, the sample at 24 hours after the prior dose must be drawn before the next dose is given and can serve as the predose sample for the next dose as long as administered within the subsequent 30 minutes.

The syringe, filter, and extension tubing should be connected after disconnecting the IV as close to the patient as possible. On Day 28, collect samples for analysis of pGSN levels and antibodies against pGSN.

Number of subjects (enrolled):

A total of 32 (6 rhu-pGSN and 2 placebo recipients per dose cohort x 4 dosing levels)

Major inclusion criteria:

1. Age ≥ 18 years

2. Gender: either
3. Informed consent obtained from subject
4. Domicile: home, assisted living, rehabilitation facility, or nursing home (as long as the prospective participant is capable of providing written informed consent)
5. Duration of infection precipitating hospitalization by history <14 days
6. Planned or actual admission to hospital with a primary diagnosis of CAP within 24 hours of presentation to the hospital
7. Primary admitting diagnosis of pneumonia supported by a compatible clinical presentation with a documented infiltrate consistent with pneumonia on chest radiograph or CT, as assessed by the admitting emergency-department (ED), clinic, or ward physician or equivalent caregiver
 - Recommended (not mandatory) guidance/discretionary criteria defining patients with CAP:
 - At least 2 symptoms: difficulty breathing, cough, production of purulent sputum, chest pain
 - At least 2 vital sign abnormalities: fever, tachycardia, tachypnea

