- ^d Doses in the multiple-dose arms should be given at 24-hour (\pm 60-minute) intervals. Blood for PK will be drawn within 30 minutes predose, 5-10 minutes after the end of administration, and 2, 8, 12 and/or 16, and 24 hrs (\pm 30 minutes) after the end of administration. Sampling at both the 12- and 16-hour time points is encouraged where feasible, but only one of these two times is required. In the multiple-dose arms, the sample at 24 hours after the prior dose must be drawn before the next dose is given and can serve as the predose sample for the next dose as long as administered within the subsequent 30 minutes. Samples are spun and plasma frozen and sent to a central lab for analysis.
- ^e Identical blood collection for PK analysis is encouraged on Day 3 but not required. Where feasible, the last PK sample would occur on Day 4 (i.e., 24 hours after the end of administration on Day 3); otherwise, because there is no study drug administered after Day 3, no further PK sampling would be done on Day 4. Samples are spun and plasma frozen and sent to a central lab for analysis.
- ^f A 10-mL aliquot (equal parts serum and plasma) will be frozen for subsequent biomarker analysis including, but not limited to, procalcitonin, pGGSN, TNF α , TGF β , IL1 β , IL1 α , IL2, IL4, IL6, IL10, IL17a levels and sent to a central lab for analysis.
- ^g Sample to be sent to a central lab for analysis.
- ^h Subjects are to be monitored for administration site reactions during study drug administration and for 1 hour after its completion.
- ⁱ The third dose of study drug may be given in a monitored outpatient setting where appropriate.
- ^j Day 1 is the first day of study treatment. Baseline tests (including blood draws) should be performed prior to administration of the first dose.
- ^k Test/assessment does not have to be repeated if performed within the prior 36 hours unless dictated by standard of care.

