9.3. Pharmacokinetic Assessments

For the one dose in the SD arm and the first 2 doses in the MAD arms, blood will be drawn within 30 minutes predose, and 5-10 minutes after the end of administration, as well as 2, 8, 12 and/or 16, and 24 hours after the end of administration (\pm 30 minutes) for analysis of plasma for C_{max} , T_{max} , $T_{1/2}$, AUC_{0-8} , AUC_{inf} . Sampling at both the 12- and 16-hour time points is encouraged where feasible, but only one of these two times is required. Identical PK sampling is encouraged on Day 3 where feasible but not required in the multiple-dose arms.

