Subject Number	Day	Date/Time of Dose on Dosing Day (DDMMYYYY/HH:MM)	Sampling Time	Was PK Sample Collected?	Date of PK Sample Collection (DDMMYYYY)	Time of PK Sample Collection (HH:MM)	Time Deviation	Concentration (ng/mL)	Change from Pre-Injection Day 1	Change from Pre-Injection) - (Mean Placebo Change from Pre-Injection)	Comments
XXX	1	DDMMYYYY/HH:MM	Pre-Injection	Yes	DDMMYYYY	HH:MM	xx mins	XXX	XXX	YYYYYY	
			5 to 10 mins post	Yes	DDMMYYYY	HH:MM	xx mins	XXX	X.XX	X.XX	
			2 hours post	Yes	DDMMYYYY	HH:MM	xx hours	XXX	X.XX	X.XX	
			8 hours post	Yes	DDMMYYYY	HH:MM	xx hours	XXX	X.XX	X.XX	
			12 hours post	Yes	DDMMYYYY	HH:MM	xx hours	XXX	X.XX	X.XX	
			16 hours post	Yes	DDMMYYYY	HH:MM	xx hours	XXX	X.XX	X.XX	
			24 hours post	Yes	DDMMYYYY	HH:MM	xx hours	XXX	X.XX	X.XX	
XXX	1	DDMMYYYY/HH:MM	Pre-Injection	Yes	DDMMYYYY	HH:MM	xx mins	XXX	XXX	YYYYYY	
			5 to 10 mins post	Yes	DDMMYYYY	HH:MM	xx mins	XXX	X.XX	X.XX	
			2 hours post	Yes	DDMMYYYY	HH:MM	xx hours	XXX	X.XX	X.XX	
			8 hours post	Yes	DDMMYYYY	HH:MM	xx hours	XXX	X.XX	X.XX	
			12 hours post	Yes	DDMMYYYY	HH:MM	xx hours	XXX	X.XX	X.XX	
			16 hours post	Yes	DDMMYYYY	HH:MM	xx hours	XXX	X.XX	X.XX	
			24 hours post	Yes	DDMMYYYY	HH:MM	xx hours	XXX	X.XX	X.XX	

Clinical cut-off date: DDMMYYYY

Program: filepath\_name, Output: filepath\_name (version x.x) Created: DDMMYYYY HH:MM

Listing 16.2.6.2.2 MAD: Individual Estimated Plasma rhu-pGSN Concentrations (unit)  
 Protocol: BTI-201  
 Intent-to-Treat Population

Cohort 1: rhu-pGSN 6 mg/kg

Subject Number	Day	Date/Time of Dose on Dosing Day (DDMMYYYY/HH:MM)	Sampling Time	Was PK Sample Collected?	Date of PK Sample Collection (DDMMYYYY)	Time of PK Sample Collection (HH:MM)	Time Deviation	Concentration (ng/mL)	Change from Pre-Injection Day 1	(Change from Pre-Injection) - (Mean Placebo Change from Pre-Injection)	Comments
XXX	1	DDMMYYYY/HH:MM	Pre-Injection	Yes	DDMMYYYY	HH:MM	xx mins	XXX			YYYYYYYY
			5 to 10 mins post	Yes	DDMMYYYY	HH:MM	xx mins	XXX	X.XX	X.XX	
			2 hours post	Yes	DDMMYYYY	HH:MM	xx hours	XXX	X.XX	X.XX	
			8 hours post	Yes	DDMMYYYY	HH:MM	xx hours	XXX	X.XX	X.XX	
			12 hours post	Yes	DDMMYYYY	HH:MM	xx hours	XXX	X.XX	X.XX	
			16 hours post	Yes	DDMMYYYY	HH:MM	xx hours	XXX	X.XX	X.XX	
			24 hours post	Yes	DDMMYYYY	HH:MM	xx hours	XXX	X.XX	X.XX	
	2	DDMMYYYY/HH:MM	Pre-Injection	Yes	DDMMYYYY	HH:MM	xx mins	XXX			
			5 to 10 mins post	Yes	DDMMYYYY	HH:MM	xx mins	XXX	X.XX	X.XX	YYYYYYYY
			2 hours post	Yes	DDMMYYYY	HH:MM	xx hours	XXX	X.XX	X.XX	

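### At 12 h, 16 h and on Day 3 the double-delta formula can difference placebo means taken over different subjects, and it then conflicts with the SAP's own output shells

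*SAP*

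**What the plan says.** **Formula.** SAP Section 9.2, Double Delta Analysis, takes each active subject's change from that day's pre-dose value and subtracts a placebo term: "Mean Placebo Treatment Group Concentration on Day z at Time Point y" less "Mean Placebo Day z Pre-dose Concentration". It does not say which placebo subjects enter either mean.

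**Shells.** For the same output, mock Listings 16.2.6.2.1 and 16.2.6.2.2 label the placebo term "Mean Placebo Change from Pre-Injection", and mock Tables 14.2.1.4 and 14.2.1.5 use the same label. That is an average of within-subject changes.

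**Sampling.** For the single dose and the first two multiple doses, samples pre-dose and at 5-10 min, 2, 8 and 24 h are required. For the other two times, Protocol 9.3 says: "Sampling at both the 12- and 16-hour time points is encouraged where feasible, but only one of these two times is required". For Day 3, SAP Section 9 says: "Identical PK sampling is encouraged on Day 3 where feasible (but not required) in the multiple-dose arms". Under Protocol Table 6, footnote d, the 24 h sample after one dose "can serve as the predose sample for the next dose as long as administered within the subsequent 30 minutes".

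**Placebo group.** Two subjects in each of four cohorts (Protocol 7.1), combined into one group (SAP Section 3).

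**Missing PK values.** SAP Section 3 rules out imputation. SAP Section 14 says missing PK points will be imputed and refers to Section 9, which covers only values below the quantitation limit.

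**The concern.** The purpose of the second delta is to remove the drift in endogenous pGSN over the day. A mean of within-subject changes does that. A difference of two separate means does it only if the same people contribute to both. Otherwise the term also carries the difference in pre-dose level between the placebo subjects sampled at that time and the whole placebo group. With so few placebo subjects, that difference need not be small.

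The same offset is subtracted from every active subject's concentration at that day and time, so averaging over active subjects does not remove it from the concentration summaries. Two programmers, one following the text and the other the shell, would report different values. PK is the study's secondary objective, and this is one of two methods the SAP uses to estimate exogenous rhu-pGSN.

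**Working it through.** The documents give no standard deviation, correlation or standard error for the placebo correction, so there is no planned figure to reproduce.

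**Inputs.** Placebo subjects: 2 x 4 = 8 on Day 1, which matches the pooled placebo row of SAP Table 1, and 2 x 3 = 6 on Days 2-3. Endogenous pGSN: Protocol 4.3 gives 200-300 mg/L as normal. Assumed: between-subject SD *s* = 30-75 mg/L, within-subject correlation *rho* = 0.3-0.9, half of the placebo subjects sampled at the time in question, and missingness unrelated to level.

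**Step 1: where the sets can differ.** If the same subjects contribute at both times, the difference of means equals the mean of differences exactly. On Days 1-2 that covers 5-10 min, 2, 8 and 24 h, provided no required sample is missed. The sets can differ at 12 h and 16 h, and at every Day 3 post-dose time. On Day 3 a subject can supply a pre-dose value (the 24 h sample after dose 2) and no post-dose sample.

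**Step 2: gap between text and shell.** Let *n* placebo subjects have a pre-dose value and *m* of them a sample at time *y*. Then

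text term = mean paired change + *d*, where *d* = (pre-dose mean of the *m*) - (pre-dose mean of the *n*).

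SD(*d*) = *s* x sqrt(1/*m* - 1/*n*), whatever the correlation.

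- 4 of 8: sqrt(1/4 - 1/8) = 0.354; x 30 to 75 = 10.6 to 26.5 mg/L.
- 3 of 6: sqrt(1/3 - 1/6) = 0.408; x 30 to 75 = 12.2 to 30.6 mg/L.

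For scale, if plasma volume is 40-50 mL/kg (assumed), 6 mg/kg raises the concentration at first by 6/0.050 to 6/0.040 = 120-150 mg/L, and by less at 12-16 h.

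**Step 3: total standard error of the placebo term.** The gap is not the net loss of precision, because pairing uses fewer pre-dose values.

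- As written: Var = *s*² (1/*m* + 1/*n* - 2 *rho*/*n*)
- Paired: Var = 2 *s*² (1 - *rho*)/*m*
- Excess as written: *s*² (2 *rho* - 1)(1/*m* - 1/*n*), positive only if *rho* > 0.5

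Standard errors in units of *s*:

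| Sampled | rho | As written | Paired | Ratio |
|---|---|---|---|---|
| 8 of 8 | 0.7 | 0.274 | 0.274 | 1.00 |
| 4 of 8 | 0.3 | 0.548 | 0.592 | 0.93 |
| 4 of 8 | 0.5 | 0.500 | 0.500 | 1.00 |
| 4 of 8 | 0.7 | 0.447 | 0.387 | 1.15 |
| 4 of 8 | 0.9 | 0.387 | 0.224 | 1.73 |
| 3 of 6 | 0.7 | 0.516 | 0.447 | 1.15 |
| 3 of 6 | 0.9 | 0.447 | 0.258 | 1.73 |

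Simulation with 200,000 replicates, run for five of these settings, agreed to within 0.002.

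**Step 4: AUC0-t on Days 1-2.** Suppose half of the placebo subjects give only the 12 h sample and half only the 16 h sample. The placebo offsets are then +*d* at 12 h and -*d* at 16 h. By the linear trapezoid (an approximation, since the SAP names a log-down, linear-up rule), the weight is 8 h on a lone 12 h or 16 h point, and 4 h and 6 h when both are present. The placebo offset carried into an active subject's AUC0-t is:

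- 12 h only: +8*d*
- 16 h only: -8*d*
- both: 4*d* - 6*d* = -2*d*

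**The case against.** The strongest reply is that little is exposed. The formula names no subject set, so it permits a mismatch without prescribing one. With the required samples complete, Days 1-2 AUC0-8 is untouched, and so is Cmax unless the peak after an IV push falls at 12 or 16 h. AUC0-t is not among the parameters the protocol lists by name, although that list is open. The shells belong to the same SAP and can be read as clarifying the text. The SAP also plans a parallel estimate with no placebo term, yielding the same three parameters, against which a shift would show. Half-missing sampling is an assumption, since both samples are encouraged. At 12 and 24 mg/kg the expected rise is two and four times larger, so the relative effect is smaller. If the correlation is below 0.5, pairing is slightly less precise.

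All of this stands, and it limits the point. It does not supply the missing same-subject rule, and it does not make text and shell agree when samples are missing. The conflicting statements on missing PK values leave that case open too.

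**Conclusion.** The point holds for the 12 h and 16 h concentrations and AUC0-t on Days 1-2, and for all Day 3 double-delta parameters. There the SAP text and its shells define different quantities whenever the placebo sets differ. The SD of the difference is about 11-27 mg/L (4 of 8) or 12-31 mg/L (3 of 6), resting on an assumed SD of 30-75 mg/L and half sampling. The standard error as written is 15% larger than the paired one at a correlation of 0.7 and 73% larger at 0.9, but 7% smaller at 0.3. A correlation above 0.5 is plausible for an endogenous protein within 24 hours, but the documents give none.

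On Day 3 there is a further reason to pair. If placebo subjects with post-dose samples differ systematically in level from those with only a pre-dose value, the formula as written is biased by that difference, and pairing removes it.

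A reader might infer three stronger claims that the documents do not support:

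- **That every corrected concentration is affected.** The required times on Days 1-2 are not, if sampling is complete.
- **That 11-27 mg/L is the precision lost.** It is the gap between the two versions; the net change in standard error is smaller and can reverse.
- **That AUC0-t moves together in all dose groups.** On Days 1-2 the 12 h and 16 h offsets can have opposite signs, so the shift depends on which samples each active subject has, and part of it can average out.

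**What to change.** 1. In SAP Section 9.2, Double Delta Analysis, define the placebo term as the mean of within-subject placebo changes from that day's pre-dose value at time *y*, using only placebo subjects with both samples, as the shells label it. Report the placebo n at each day and time.
2. In the section on the pre-dose and placebo adjusted ratio, state the same rule on the log scale (mean within-subject log change). That formula does not say how placebo values are averaged or paired.
3. Reconcile SAP Sections 3, 9 and 14 on missing PK values.

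The cost is SAP wording and one n per time point; the shell labels already fit. The downside is that fewer placebo pre-dose values are used, which slightly raises the standard error if the within-subject correlation is below 0.5.
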